3.1. Per Protocol Set Analysis Set (PPS)

The per protocol set (PPS) includes all randomized subjects who have received both doses of vaccine and who do not meet the following exclusion criteria:

1. Have a positive SARS-CoV-2 central serology result prior to the first dose of vaccine.
2. Receive a positive Reverse Transcription Polymerase Chain Reaction (RT-PCR) diagnostic test result for SARS-CoV-2 infection at any time point prior to the scheduled visit 56 days after the first dose of vaccine.
3. Receive any dose of investigational or approved passive antibodies for SARS-CoV-2 infection prophylaxis (eg, convalescent plasma or sera, mAbs, hyperimmune globulin) outside of the study at any time point prior to the scheduled visit 56 days after the first dose of vaccine.
4. Receive any other vaccine within 28 days prior to the study to the scheduled visit 56 days after the first dose of Moderna mRNA-1273 vaccine administered as part of this study.

Exception: seasonal influenza vaccine is only prohibited within 14 days before or after study drug administration, or within 14 days before or after Moderna mRNA-1273 vaccine administration.

5. Receive systemic medications that suppresses the immune system (for corticosteroids, ≥ 20 mg/day of prednisone equivalent) at any time point prior to the scheduled visit 56 days after the first dose of vaccine.
6. Receive IVIG or blood products at any time point prior to the scheduled visit 56 days after the first dose of vaccine.
7. Subjects with incomplete infusions or injections of study drug or vaccine at any time point prior to the scheduled visit 56 days after the first dose of vaccine.
8. Subjects with baseline neutralization antibody titer above the lower limit of quantification (LLOQ).

The PPS is the primary analysis set for assessing vaccine response related endpoints.

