4.5. Vaccine Response Variable

4.5.1. Primary Vaccine Response Variable

The primary endpoint is the 50% inhibitory dilution (ID50) neutralizing antibody titers of vaccine-induced neutralizing antibodies to SARS-CoV-2, assessed 56 days after the first dose of the vaccine (ie, the vaccine response assessment period). The 56-day time point corresponds to study day 71 for study arms 1, 2, 3, 7, 8, 6a, and 6c, and study day 57 for study arms 4, 5, 9, 6b, and 6d.

The Neutralizing Antibody Assay (IMMUNO-COV REGN2118) is a functional assay that detects the presence of specific neutralizing antibodies capable of inhibiting vesicular stomatitis virus (VSV)- SARS2-Fluc. Infection by VSV-SARS2-Fluc results in the expression of firefly luciferase within Vero cells overexpressing the Ace-2 receptor (Vero-Ace-2). Luciferase substrate (d-luciferin) is added to assay plates to allow for a luminescence readout. The total luminescence (relative light units, RLU) corresponds to the extent of infection by VSV-SARS2-Fluc. The ability of antibodies in human serum to block infection of Vero-Ace-2 cells by VSV-SARS2-Fluc by 50% serves as a proxy readout for antibodies capable of neutralizing SARS-CoV-2 infection.

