5.7. Analysis of Vaccine Response Variables

For efficacy variables, baseline is defined as the last available value prior to the first dose of Moderna mRNA-1273 vaccine. The analyses will be conducted based on the observed data with no imputation for missing data. Values below the LLOQ will be set to half of LLOQ and values above the upper limit of quantification (ULOQ) will be set to the ULOQ.

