6.1. Definition of Baseline

Unless otherwise specified, the baseline assessment for all measurements will be the latest available valid measurement taken prior to the administration of the first dose of Moderna mRNA-1273 vaccine or REGN10933+REGN10987 (as applicable and whichever occurs first).

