6.2. Data Handling Convention for Vaccine Response Variables

Values below the LLOQ will be set to half of LLOQ and values above the upper limit of quantification (ULOQ) will be set to the ULOQ. If two or more measurements correspond to the same visit, the lowest value will be used.

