6.4. Analysis Windows

Assessments repeatedly collected during the study will be defined by the eCRF visit label for temporal tabulations and subject listings.

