6.5. Unscheduled Assessments

For safety variables unscheduled visit measurements may be used to determine abnormal values, and PCSVs.

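### Using the lowest result when a visit has repeats biases those titres downward in expectation, including the primary day-56 ID50; the arm comparison is affected only if repeats or assay error are uneven

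*SAP*

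**What the plan says.** The convention is in SAP 6.2, beside the rules for results outside the quantification limits (half the LLOQ below, the ULOQ above): "If two or more measurements correspond to the same visit, the lowest value will be used". The section covers vaccine response variables in general. SAP 4.5.1 and 5.7.1 name the day-56 ID50 titre as the primary one, and nothing exempts it. No reason for the rule and no sensitivity analysis are given. Protocol 11.4.3 covers values below the LOQ and missing data but has no rule for duplicates, so the SAP sentence governs.

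Visits are identified by label in SAP 6.4: "Assessments repeatedly collected during the study will be defined by the eCRF visit label for temporal tabulations and subject listings". SAP 6.5 mentions unscheduled measurements for safety variables only.

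Baseline is chosen by time. SAP 5.7: "For efficacy variables, baseline is defined as the last available value prior to the first dose of Moderna mRNA-1273 vaccine". SAP 6.1 gives the general rule as "the latest available valid measurement taken prior to the administration of the first dose of Moderna mRNA-1273 vaccine or REGN10933+REGN10987", whichever comes first. PPS criterion 8 in SAP 3.1 then excludes subjects whose baseline neutralising titre exceeds the LLOQ.

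SAP 6.1 requires a valid measurement. SAP 6.2 does not use that word.

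**The concern.** The rule selects on the outcome. If two results for one visit are the true titre plus independent error, the smaller is on average below the true titre, and more so with more results. The sentence also has no validity condition, so as written a spuriously low result always wins over a correct one.

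The study plans no hypothesis test (Protocol 11.1), so the estimates and their intervals are the result. SAP 5.7.1 reports a geometric mean for each group and a relative difference for each antibody arm against the pooled vaccine-only group. The group means move down with any untied repeats. The relative differences move only if repeats are unevenly spread or the error differs, and then in either direction: extra repeats in an antibody arm would exaggerate interference, and extra repeats in controls would hide it. One primary objective is to find an interval with no meaningful impact on the vaccine response, so both directions matter.

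**Working it through.** **Inputs from the documents.** SD of the log10 titre 0.30; 30 subjects per antibody arm and 46 pooled controls; 95% half-width for arm versus pooled controls 0.14 (Protocol 11.2, SAP 2.2).

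**Inputs assumed.** The within-subject assay SD, s, is taken as 0.05 to 0.20 log10, with 0.10 to 0.20 as the main range. The repeat rate is varied. The documents give neither, nor do they say whether repeats would be re-assays or new draws.

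**Step 1: the plan's half-width.** With 9 groups and 286 subjects there are 277 residual degrees of freedom, and t = 1.969. Half-width = 1.969 × 0.30 × √(1/30 + 1/46) = 0.139, which agrees with 0.14.

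**Step 2: bias of one repeated result.** For two independent normal errors, E[min] − true value = −s/√π = −0.564 s. For three it is about −0.846 s. A simulation of 400,000 draws agreed with both.

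| Assumed s (log10) | Lowest of two (log10) | Change in titre | Lowest of three (log10) |
|---|---|---|---|
| 0.05 | −0.028 | −6% | −0.042 |
| 0.10 | −0.056 | −12% | −0.085 |
| 0.15 | −0.085 | −18% | −0.127 |
| 0.20 | −0.113 | −23% | −0.170 |

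The mean of the log titres, which is the geometric mean, has expected bias 0 (simulated: 0.0001 at s = 0.10). The percentages do not depend on the log base, so they carry over to the base-2 model in SAP 5.7.1. Results that tie, for example both at half the LLOQ or both at the ULOQ, are not shifted.

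**Step 3: bias of a group mean.** This is the share of subjects with a pair times the Step 2 bias. At s = 0.10 and 20% repeats: 0.20 × 0.056 = 0.011 log10, a geometric mean about 2.6% lower.

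**Step 4: bias of arm versus pooled controls.** With the same error in both groups, this is −(arm repeat rate − control repeat rate) × 0.564 s.

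- Equal rates: 0.
- 10% against 0%, s = 0.10: 0.10 × 0.056 = 0.006 log10 (ratio −1.3%), or 0.006/0.14 = 4% of the half-width.
- 30% against 0%, s = 0.20: 0.30 × 0.113 = 0.034 log10 (ratio −7.5%), or 0.034/0.14 = 24% of the half-width.

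**Step 5: a route that needs no drug effect.** By target, 30 of the 46 pooled controls are in waves 1 and 2, while arms 7 to 9 are in waves 3 and 4. Suppose, as an illustration only, that 20% of subjects had repeats in waves 3 and 4 and none in waves 1 and 2. The pooled-control rate would be 0.20 × 16/46 = 7.0%, the gap 13.0%, and the bias for arms 7 to 9 would be 0.130 × 0.056 = 0.007 log10 at s = 0.10, or 0.015 at s = 0.20.

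**Step 6: baseline.** SAP 5.7 and 6.1 pick the last or latest value. That may not separate two assays of the same draw, and the SAP does not say whether 6.2 then decides. A geometric mean would not fully settle criterion 8 either: one result below the LLOQ (set to 0.5 LLOQ) and one at 1.5 LLOQ give √(0.5 × 1.5) = 0.87 LLOQ, which still passes.

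**The case against.** The strongest reply is that the rule is identical in every arm, so equal repeat rates and equal error leave the primary contrast unbiased. That stands.

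Nothing shows that repeats are common. The schedules list one neutralisation serum entry per visit, and unscheduled visits have their own column, so an unscheduled draw would not normally carry the day-56 label. Even the assumed range is small: 0.034 log10 is 2.4% of the 1.44 log10 drop that SAP 2.2 cites as a benchmark. These points limit the severity, but they do not justify choosing a result by its value.

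Two stronger readings are tempting. A reader might infer that the antibody arms are biased low because the anti-idiotype step leads to more re-runs at high drug levels. The documents describe that step (Protocol 3.2.1.5 and 9.2.3.1) but say nothing about re-run rates, so this is conjecture. A reader might also infer that the lowest value decides baseline titre and hence entry to the PPS. SAP 5.7 and 6.1 choose baseline by time, so what remains is an unstated interaction for same-visit repeats. Criterion 1, on central serology before vaccination, is also a separate screen.

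Finally, a change now comes after data have been seen. The Protocol's Amendment 5 history reports an interim analysis of waves 1 and 2. The SAP's change log mentions only ULOQ handling for section 6.2, which suggests that the lowest-value rule was already in version 1. This stands, and it is why the existing rule should stay as a sensitivity analysis.

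**Conclusion.** The point holds for the measurement and for the reported group geometric means. A visit with two untied results is biased low in expectation by 0.056 to 0.113 log10 (12% to 23% in titre) if the assay SD is 0.10 to 0.20 log10 and the errors are independent and normal. For the arm-to-control ratio it is conditional: no bias with equal repeat rates and equal error, and 0.006 to 0.034 log10 if 10% to 30% of one arm and no controls have repeats. The documents neither show nor exclude such an imbalance, and they do not support a claim that the primary comparison is biased, in either direction. The sample-size justification does not change. For baseline and PPS criterion 8, the finding is only that the passages need to be reconciled.

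**What to change.** 1. Replace the sentence in SAP 6.2 with: *Where a visit has two or more valid results, their geometric mean will be used.*
2. Report the number of subjects with repeats, by arm, for the primary visit.
3. Repeat the primary analysis under the lowest-value rule as a sensitivity analysis, so that results can be compared with any interim results derived that way.
4. Reconcile SAP 6.2 with the time-based baseline rules in 5.7 and 6.1. State how same-visit baseline repeats are handled for PPS criterion 8, including whether a single valid result above the LLOQ is enough to exclude; averaging alone leaves that open.

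This is a cheap improvement: a few lines of SAP text, one table and one re-run, with no new data or subjects. The small downside is a primary-variable derivation that may differ from the one used at the interim analysis, so the change and its reason should be recorded in the SAP's revision history.

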6.3. Data Handling Convention for Missing Data

Adverse Event

If the severity of a TEAE is missing, it will be classified as severe in the frequency tables by intensity of TEAEs.

If the assessment of relationship of a TEAE to either Moderna mRNA-1273 vaccine or REGN10933+REGN10987 is missing, following rules will be applied

- If the relationship to Moderna mRNA-1273 vaccine is missing, the TEAE will be classified as related to Moderna mRNA-1273 vaccine if the TEAE occurs after the first dose of vaccine
- If the relationship to REGN10933+REGN10987 is missing, the TEAE will be classified as related to REGN10933+REGN10987 if the TEAE occurs after the REGN10933+REGN10987 administration

If the start time of an AE is completely missing, it will be assumed to have occurred on the time of the first dose of Moderna mRNA-1273 vaccine or REGN10933+REGN10987 (as applicable and whichever occurs first). When the partial AE time information does not indicate that in which period (pre-treatment/pre-vaccination/vaccination/post-vaccination) the AE starts, the following rules will be applied (1) if the AE could happen either in pre-treatment or pre-vaccination periods, the AE will be classified to the pre-vaccination period (applicable to arms 1, 2, 3, 4, 5, 7, 8); (2) if the AE could happen either in pre-treatment or vaccination periods, the AE will be classified to the vaccination period (applicable to arms 6a – 6d and 9); (3) if the AE could happen either in pre-vaccination or vaccination periods, the AE will be classified to the vaccination period (applicable to arms 1, 2, 3, 4, 5, 7, 8); (4) if the AE could happen either in vaccination or post-vaccination periods, the AE will be classified to the vaccination period. If the end date of the AE is missing, then the date of the last follow-up will be used for imputation.

Medication/Procedure

If a medication time is missing or partially missing and it cannot be determined whether it was taken prior or concomitantly or stopped prior to the first dose of Moderna mRNA-1273 vaccine

or REGN10933+REGN10987 (as applicable and whichever occurs first), it will be considered as concomitant medication/procedure by imputing the start time on the time of first dose of Moderna mRNA-1273 vaccine or REGN10933+REGN10987 (as applicable and whichever occurs first).

Potentially Clinically Significant Values

If a subject has a missing baseline value, this subject will be grouped in the category “normal/missing at baseline.”

For PCSVs with 2 conditions, one based on a change from baseline value and the other on a threshold value or a normal range, with the first condition being missing, the PCSV will be based only on the second condition.

For a PCSV defined on a threshold and/or a normal range, this PCSV will be derived using this threshold if the normal range is missing; e.g., for eosinophils the PCSV is >0.5 giga/L or $>\text{ULN}$ if $\text{ULN} \geq 0.5$ giga/L. When ULN is missing, the value 0.5 should be used.

Measurements flagged as invalid by the laboratory will not be tabulated or taken into account in the computation of PCSVs.

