9.2.2. Study Drug and Vaccine Administration and Post-Administration Monitoring

Refer to Section 8.5 for treatment assignments.

SC and IM Injection Administration

All subjects allocated to a SC regimen will receive either 4 (study arm 4) or 2 (study arm 5) injections of study drug on the day of administration. It is recommended that SC injection sites should be chosen among the different quadrants of the abdomen (avoiding navel and waist areas) and upper thighs. During study drug administration, each injection must be given in a different anatomical location (1 injection administered in the right lower quadrant of the abdomen, another in the left lower quadrant of the abdomen, etc).

All subjects will receive each Moderna mRNA-1273 vaccination dose through a single IM injection in the deltoid muscle ([CDC, 2021](#)).

Subjects should receive all doses of Moderna mRNA-1273 vaccine as assigned and as described in the EUA Fact Sheet ([Moderna COVID-19 Vaccine \[HCP Fact Sheet\], 2022](#)).

Study arms 4 and 5 only: Subjects will receive both study drug and vaccine on day 1. The study drug will be administered first, followed by the vaccine. There must be a minimum of 2 hours waiting period between administration of the study drug and subsequent vaccine. Administration of the individual regimens should be performed as described above.

Post-administration monitoring of study drug and vaccine

Study arms 1 through 5 and 7 through 9: Subjects should be monitored for at least 1 hour after study drug or vaccine administration. Vaccine recipients should be monitored for the occurrence of acute reactions according to the latest CDC guidelines ([CDC, 2021](#)). For study arms 4 and 5 (receiving study drug and vaccine on the same day), approximately 24 hours after completion of the study drug and vaccine administration on day 1, subjects will be followed up by telephone for safety.

Study arms 6a, 6b, 6c and 6d: Subjects assigned to each of these study arms will not receive study drug during this study. These subjects should be monitored for at least 30 minutes after vaccine administration.

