2. INVESTIGATION PLAN

2.1. Study Design and Randomization

This study is a phase 2, randomized, open-label, parallel group study in healthy adult volunteers to assess the immunogenicity, safety, and tolerability of Moderna mRNA-1273 vaccine when administered with REGN10933+REGN10987.

At screening, eligible subjects were to be assigned to an enrollment wave. The enrollment waves were intended to avoid or minimize the potential for unused doses of Moderna mRNA-1273 COVID-19 vaccine (Protocol Section 3.2.1 for additional rationale). Every effort was made by sites to avoid unused doses of vaccine.

Every effort was made by the site to ensure balance of age (<65 years and \geq 65 years) within each of the enrollment waves. At baseline (day 1), subjects were to be randomized to the corresponding study arms in each wave as described in [Table 1](#).

Randomization was performed according to a computer-generated randomization scheme provided by an interactive web response system (IWRS) to a designated study pharmacist or a qualified designee.

Randomization was stratified by age (<65 years versus \geq 65 years).

Table 1: Study Treatment Assignment

Study Arm	Randomization Ratio	Targeted Enrollment	Co-administered REGN10933+REGN10987 Combination Therapy	Moderna mRNA-1273 Vaccine*
Enrollment Wave 1				
1	2	30	1200 mg (600 mg of each mAb) IV on day 1	On day 15 and day 43
2	2	30	300 mg (150 mg of each mAb) IV on day 1	On day 15 and day 43
3	2	30	150 mg (75 mg of each mAb) IV on day 1	On day 15 and day 43
6a	1	15	None	On day 15 and day 43
Enrollment Wave 2				
4	2	30	1200 mg (600 mg of each mAb) SC on day 1	On day 1 and day 29
5	2	30	600 mg (300 mg of each mAb) SC on day 1	On day 1 and day 29
6b	1	15	None	On day 1 and day 29
Enrollment Wave 3				
7	15	30	48 mg (24 mg of each mAb) IV on day 1	On day 15 and day 43
8	15	30	12 mg (6 mg of each mAb) IV on day 1	On day 15 and day 43
6c	4	8	None	On day 15 and day 43
Enrollment Wave 4				
9	15	30	1200 mg (600 mg of each mAb) IV on day 7	On day 1 and day 29

6d	4	8	None	On day 1 and day 29
----	---	---	------	---------------------

*Moderna mRNA-1273 vaccine will be administered as described on the US FDA EUA HCP Fact Sheet, 2021)
mAb=monoclonal antibody; SC=subcutaneous; IV=intravenous.

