4.6. Safety Variables

4.6.1. Adverse Events and Serious Adverse Events

Adverse events and serious adverse events will be collected from the time of informed consent signature and then at each visit until the end of the study. All adverse events are to be coded to a PT and associated SOC according to the latest version of MedDRA®.

For safety variables, the following observation periods are defined:

- The **pre-vaccination period** is defined as the time from study drug administration to the first vaccine dose administration.
- The **primary series vaccination period** is defined as the time from the first vaccine dose administration to 28 days after the second vaccine dose administration, and in subjects receiving only one dose of the vaccine, 28 days after the first vaccine dose administration.

- The **post primary series vaccination period** is defined as the time from the end of the primary series vaccination period to the end of the follow-up period in subjects who do not receive the sub-study provided vaccine booster. In subjects who receive the sub-study provided vaccine booster dose, the post-primary series vaccination period is defined as the time from the end of the primary series vaccination period to the administration of the sub-study provided vaccine booster.
- The **post-booster vaccination period** is defined as the time from the sub-study provided vaccine booster to the end of the follow-up period.

Treatment-emergent adverse events are defined as those that are not present at the time of the first dose of Moderna mRNA-1273 Vaccine or REGN10933+REGN10987 (as applicable and whichever occurs first) or represent the exacerbation of a pre-existing condition.

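### SAP 6.3 puts an adverse event with no start date before vaccination in arms given drug first, but in the vaccination period in controls and arm 9, contrary to its own rule for partly dated events (low priority)

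*SAP*

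**What the plan says.** SAP 6.3 has separate conventions for AE starts that are completely missing and those that are partly missing.

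- **Completely missing:** "If the start time of an AE is completely missing, it will be assumed to have occurred on the time of the first dose" of vaccine or REGN10933+REGN10987, "as applicable and whichever occurs first".
- **Partly missing:** four period rules apply. Rule (3), stated for arms 1, 2, 3, 4, 5, 7 and 8, reads: "if the AE could happen either in pre-vaccination or vaccination periods, the AE will be classified to the vaccination period".
- **Missing causality:** an event with no recorded relationship to study drug "will be classified as related to REGN10933+REGN10987 if the TEAE occurs after the REGN10933+REGN10987 administration". A parallel rule makes it vaccine-related if it occurs after the first vaccine dose.

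SAP 4.6.1 sets the periods. For the pre-vaccination window its wording is: "is defined as the time from study drug administration to the first vaccine dose administration". The next window, covering the primary series, opens at vaccine dose one and closes 28 days after dose two, with a shorter version for subjects given one dose. SAP 5.8.1 tabulates AEs by treatment group for all periods combined and separately for the pre-vaccination, primary series and post-booster periods.

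**The concern.** Which product comes first depends on the arm, so the same undated event goes to different periods in different arms. Controls receive only the vaccine and have no pre-vaccination period, so their undated events always enter the vaccination-period tables. In arms given drug first they do not. Those tables set vaccine plus drug beside vaccine alone from the first vaccine dose onward, so they bear on the secondary objective of tolerability in close succession (SAP 1.2.2).

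The convention also runs against its neighbour. In the same seven arms, an event with some date information is resolved towards the vaccination period, and one with none is resolved away from it. Because the missing-causality rules depend on timing, the imputed date also decides which product an unattributed event can be charged to.

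**Working it through.** **1. Group sizes.** Targets in SAP 2.1, Table 1: 8 drug arms × 30 = 240; controls 15 + 15 + 8 + 8 = 46; total 286. This reproduces the planned enrolment in SAP 2.2.

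**2. Placement by arm.** The missing-start rule is applied to each dosing order.

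| Arms | Dosing order | Imputed start | Period | Planned n |
|---|---|---|---|---|
| 1, 2, 3, 7, 8 | drug day 1; vaccine "On day 15 and day 43" | drug, day 1 | pre-vaccination | 150 |
| 4, 5 | both day 1, at least 2 hours apart | drug, day 1 | pre-vaccination if a clock time is imputed; undetermined by date alone | 60 |
| 9 | vaccine day 1, drug day 7 | vaccine, day 1 | primary series vaccination | 30 |
| 6a to 6d | vaccine only | vaccine, day 1 or 15 | primary series vaccination | 46 |

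The order in arms 4 and 5 is fixed by Protocol 9.2.2: "The study drug will be administered first, followed by the vaccine".

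**3. Comparison with rule (3).** A partial date that leaves pre-vaccination and vaccination both possible goes to vaccination in arms 1 to 5, 7 and 8. With no date at all, both are still possible, yet the event goes to pre-vaccination. The two sentences point in opposite directions in the same arms.

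**4. Start and causality both missing.** This reads an event dated at a dose as occurring after that dose.

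- Drug-first arms: the event can default to drug-related. It precedes the vaccine, so it cannot default to vaccine-related.
- Arm 9: it can default to vaccine-related. It precedes the drug, so it cannot default to drug-related.
- Controls: it can default to vaccine-related.

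This also reaches the all-periods tables of drug-related and vaccine-related TEAEs.

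**5. Size per subject.** One subject moved is 1/30 = 3.3 points in a drug arm. One control subject is 1/46 = 2.2 points if controls are pooled. SAP 5.7.1 states pooling for vaccine response; SAP 5.8.1 says only by treatment group.

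**6. Illustration.** The documents give no AE rate and no missing-date rate, so these are assumptions:

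- The true proportion p with a vaccination-period TEAE is equal in both groups, at 30%, 60% or 80%.
- A fraction m of AEs has no start date, at 1%, 5% or 10%.
- Counts are Poisson with λ = −ln(1 − p), which allows for subjects who have another dated event in the period.
- Out-of-period AEs occur at r times the in-period rate, with r = 0 or 0.5.

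Drug-first proportion: 1 − exp[−λ(1 − m)]. Control proportion: 1 − exp[−λ(1 + rm)]. For p = 60%, m = 5%, r = 0: λ = 0.916, drug-first = 1 − exp(−0.916 × 0.95) = 58.1%, control = 60.0%, difference −1.88 points.

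| p | m | Drug-first | Difference, r = 0 | Difference, r = 0.5 |
|---|---|---|---|---|
| 30% | 1% | 29.7% | −0.25 | −0.37 |
| 30% | 5% | 28.7% | −1.26 | −1.88 |
| 30% | 10% | 27.5% | −2.54 | −3.78 |
| 60% | 1% | 59.6% | −0.37 | −0.55 |
| 60% | 5% | 58.1% | −1.88 | −2.78 |
| 60% | 10% | 56.2% | −3.84 | −5.63 |
| 80% | 1% | 79.7% | −0.32 | −0.48 |
| 80% | 5% | 78.3% | −1.68 | −2.46 |
| 80% | 10% | 76.5% | −3.49 | −5.04 |

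The largest drug-arm loss, 3.84 points, is 3.84/3.33 ≈ 1.2 subjects in an arm of 30. If undated events go to the vaccination period in every arm, the artificial difference is 0.00 in each row.

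**The case against.** Dating an undated AE to the first product is a familiar way to make sure it counts as treatment-emergent, and the rule does that in every arm. The event is not lost: in drug-first arms it appears in the pre-vaccination tables, which are also by treatment group, and every AE is listed. AESIs are tabulated only for all periods combined. Safety is descriptive with no testing (Protocol 11.1). AEs are to be recorded promptly and asked about at each visit (Protocol 10.1.1), so a start with no date information at all should be rare. An undated reaction that truly began before vaccination is placed correctly by the present rule. All of this stands, and it limits the point without removing it: the period tables are planned, the placement depends on arm, and the adjacent rule says the opposite.

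A reader might infer that the safety comparison as a whole is biased in favour of the drug. The documents do not support that. The TEAE and SAE endpoints cover the whole study (SAP 1.2.4) and their counts do not move, while the drug arms' pre-vaccination counts rise. A reader might also infer that the conservative causality default is defeated. That is too broad: default attribution to drug still works in drug-first arms, and the losses in step 4 need both start and causality to be missing. Nor are all 210 subjects in the seven arms affected for certain. Arms 4 and 5 depend on an imputed clock time, and SAP 6.3 uses time and date loosely.

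**Conclusion.** The inconsistency is real and lies in the text itself. It can understate vaccination-period TEAE proportions in 150 planned drug-first subjects, or 210 with arms 4 and 5, relative to controls. A proportion changes only where the subject has no other qualifying TEAE in that period. It also removes one default attribution in the doubly missing case.

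The size cannot be estimated from the documents. Under the stated assumptions the artificial difference runs from −0.25 to −5.63 points, and with 1% of AEs undated it is at most −0.55. The negative sign assumes equal true risk and equal missingness across arms. No endpoint or error rate is affected. This is a low-priority correction.

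**What to change.** Replace the missing-start sentence in SAP 6.3 along these lines. For a subject who received a vaccine dose, a completely missing AE start is period-ambiguous, and the event goes to the primary series vaccination period in every arm, as rule (3) does for partial dates. The exception is a record showing onset before the first vaccine dose, such as the visit of first report or a recorded (not imputed) end date; the event then goes to the pre-vaccination period. Arm 9 and the controls have no such period, so there it would be pre-treatment. If causality is also missing, count the event as related to each study product received before it was first reported. The present rule can remain for subjects given drug but no vaccine.

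The cost is a few lines of SAP text, a derivation of the visit of first report (the SAP defines no such variable) and a small programming change. The downside is that some drug-arm events that truly began before vaccination will be counted in the vaccination period. That error is conservative for the drug, and rule (3) already accepts it.
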